**Fig. 2. Freedom from termination of fetal SVT with and without hydrops (n=75).** Treatment failure was also more likely if SVT was associated with fetal hydrops (HR=1.8; p=0.04) at the time of diagnosis. It took more than twice as long (9 vs. 4 days) for conversion of 50% of SVT cases to a normal rhythm if fetuses were hydropic. 21% of the hydropic cases died.

[figure not shown]
lower cardioversion rates. On the other hand, 1st line monotherapy with sotalol resulted in faster/higher AF termination rates [Fig. 3] while flecainide or digoxin was superior in terminating SVT [Fig. 4] and in lowering tachycardia rates if SVA persisted [Fig. 5]. None of the agents as 2nd line therapy was associated with a greater rate of SVA termination although **sotalol** tended to be superior for AF. Once fetal SVA was converted to sinus rhythm, chronic drug therapy to birth with the drug(s) that successfully terminated the SVA was used to prevent recurrences. Recurrence of SVT and AF was documented in 8% and 15% of cases during the first month of maintenance treatment.

**Fig. 3. Freedom from termination of fetal AF (n=36):** For patients with AF, in multivariate models adjusted for arrhythmia pattern, 1st line sotalol was associated with a greater likelihood of AF termination compared with digoxin (HR: 5.4; p=0.05) or flecainide (HR: 7.4; p=0.03). Time to conversion of 50% was 12 days with sotalol, but not achieved with the other drugs before delivery.

**Fig. 4. Freedom from termination of fetal SVT (n=75):** For patients with SVT, in multivariate models adjusted for hydrops and SVT pattern, the use of flecainide (HR: 2.9; p=0.01) or digoxin (HR: 2.1; p=0.02) as 1st therapy were associated with increased likelihood of SVT termination compared to sotalol. The median time to conversion of 50% of cases was 3 days with digoxin, 4 days with flecainide but 12 days with sotalol.

**Fig. 5. Effects of 1st line treatment on tachycardia rates.** When incessant SVT (n=23) or AF (n=22) persisted to day 5 of treatment, ventricular rates were lowered more with flecainide and digoxin than with sotalol (p<0.001). This suggests that flecainide and digoxin are similarly effective in reducing the tachycardia to better tolerated rates while sotalol has no or only modest heart rate slowing effects.

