however important to recognize that 1st line treatment effects are incremental and it will take several days to reach therapeutic fetal drug levels with transplacental medication. A *premature change to 2nd line therapy prior to 3-7 days of therapy is therefore not advised* unless there is significant worsening of the fetal state (e.g. new hydrops), the SVA pattern (>20% increase in SVA rates and duration), or both. Members of the FAST Trial steering committee have developed consensus-based recommendations [Care Maps] to adjust the prenatal pharmacotherapy to the most common treatment outcomes and clinical scenarios, e.g. if 1st, 2nd or 3rd line treatment appears ineffective. Care Map recommendations may include: a) no change in therapy (sinus rhythm; ↓ SVA <10% of time); b) escalation of drug dose (some SVA response); or c) addition of or change to different medication (no SVA response). The responsible physician is free to follow the recommendations or to elect treatment that differs from the Care Map. Cross over to a different medication, fetal demise, preterm delivery, and SVA that persists to birth will be considered as *1st line treatment failure*. Removal of an agent from treatment following sustained conversion to a normal rhythm (*treatment success*) does not constitute treatment failure.

Following sustained conversion to a normal rhythm of at least 24 hours (*acute 1st line treatment success*), it is recommended to not change the successful treatment until birth if the treatment is tolerated and the SVA does not recur. Any new documentation of fetal SVA on maintenance therapy that is *confirmed by fetal echocardiography or by heart rate monitoring during labor* will be considered as *maintenance treatment failure*. Near-complete suppression of SVA does usually not require a change in maintenance therapy. Maternal drug therapy will be maintained until time of delivery and discontinued immediately thereafter. The *choice of postnatal neonatal drug therapy* will be at the discretion of the primary physician. Postnatal outcomes will be assessed to a minimum of 1 month of age.

**7.8 PROCEDURES OUTSIDE OF STANDARD CARE.** The conduct of the RCT sub-studies requires procedures that are not part of usual patient management and documentation of findings. This includes:

- The process of randomization to 1st line therapy

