#### **SECONDARY OUTCOME**

- Proportion of participants with cardioversion over time
- Proportion of participants with treatment failure
  - Number of participants with treatment failure compared to number of participants with successful treatment.
  - Treatment failure is defined as one of the following:
    1. cross-over to another drug
    2. SVT/AF that persists to birth
    3. preterm birth
    4. death
- Cause of death (prenatal, postnatal)
- Proportion of participants with arrhythmia related death
- Average gestational age at birth
- Birth weight (z-scores)
- Average days of maternal and neonatal hospitalization related to SVA therapy
- Maternal prevalence of pregnancy/treatment-related AEs and outcomes
- Proportion of AEs / adverse outcomes (prenatal, postnatal)

The primary outcome measure is absolute (term delivery without tachyarrhythmia) with no room for interpretation. Secondary outcomes will be the time interval from treatment initiation to the beginning of permanent cardioversion, and once established, the freedom from SVA recurrence on maintenance therapy. Only the final outcome will be considered to classify cases. Cross-over to another agent, fetal demise, development of fetal hydrops, and delivery for SVA will be considered treatment failures. Any recurrence of fetal SVA after

documentation of a normal cardiac rhythm >24 hours by echocardiography will be classified as maintenance treatment failure.

**7.11 STATISTICAL ANALYSES.** All statistical analyses using SAS (SAS Institute, Cary NC) with standard settings will be performed by very experienced statistician from the Cardiovascular Data Management Centre (CVDMC) at SickKids. As a general precept, all 3 RCTs will be analyzed separately. RCT analyses will be performed on an *intention-to-treat basis*, although a separate subgroup analysis will be performed. Descriptive statistics for all study variables, for each study groups separately, will be created using means with standard deviation, median with inter-quartile range, and frequencies as appropriate. Baseline characteristics that should be equally distributed between groups through randomization (age at diagnosis, baseline fetal heart rate, incessant vs. intermittent SVA, maternal age) will be assessed in a test of randomization. The test of randomization will be performed using Fisher’s exact test for categorical variables and Student’s t-test (with Satterthwaite method for variance estimation) for continuous variables.

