The **PRIMARY OUTCOME** (proportion of term deliveries without SVA) will be a binary outcome (yes/no). For this type of outcome, the proportion of participants in each therapy arm will be compared using logistic regression models (PROC LOGISTIC) with likelihood ratio test to determine regression model fit, Wald chi-square test from maximum likelihood estimates (Fisher’s scoring technique) to determine statistical significance of the therapy arm and c-statistic from the regression model’s area under the curve (AUC) to measure model accuracy. Effect size estimate and standard error will be converted into odds ratio with 95% confidence (95% CI) limits to facilitate comparisons between the different trials.

**SECONDARY OUTCOME** will also be expressed as binary variables (incl. proportions of participants: requiring 2nd line therapy and 3rd line therapy; with SVA recurrence on maintenance therapy; delivery without SVA termination; death <1 month; etc.) will be assessed between the different therapy arms in the same way as the primary outcome. For outcomes with time dependent variables (proportion of participants with cardioversion over time; timing of mortality from initiation of therapy), Kaplan-Meier survival curves will be used to depict the event proportion over time for each group. Single phase parametric hazard regression model (PROC PHREG) will be used to compare the 2 therapy arms (with likelihood ratio test to determine regression model fit and maximum likelihood estimates chi-square to determine statistical significance of the therapy arm. Effect size estimate and standard error will be converted into hazard ratio with 95% CI to facilitate comparisons between the different trials. Finally, for outcomes with continuous variables (average gestational age at birth/birth weight z-score; average days of neonatal hospitalization related to SVA therapy), linear regression models using maximum likelihood estimates for parameter estimation will be used (PROC GENMOD: Akaike's information criterion (AIC) criterion to assess regression model fit; Wald chi-square test from maximum likelihood estimates). Effect size estimate and standard error will determine the difference between the therapy arms in the same original units of measurement as the outcome.

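### Recurrence on maintenance therapy is worded as freedom from recurrence in section 7.10 but tested as a yes/no outcome in 7.11, which at equal hazard counts against the drug that converts sooner and prolongs pregnancy

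*Combined protocol and SAP*

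**What the plan says.** Section 1 names the efficacy of maintenance therapy among the secondary outcomes. Section 7.10 describes the endpoint as "once established, the freedom from SVA recurrence on maintenance therapy".

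Section 7.11 (Secondary outcome) puts participants "with SVA recurrence on maintenance therapy; delivery without SVA termination; death <1 month" among the binary outcomes, which "will be assessed between the different therapy arms in the same way as the primary outcome". That means logistic regression, a Wald test and an odds ratio. The outcomes given Kaplan-Meier curves and PROC PHREG are "proportion of participants with cardioversion over time; timing of mortality from initiation of therapy". Recurrence is not among them.

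Section 7.7 (Treatment) sets the time at risk. The maintenance phase begins "Following sustained conversion to a normal rhythm of at least 24 hours", and "Maternal drug therapy will be maintained until time of delivery and discontinued immediately thereafter". Any newly confirmed SVA in that period counts, with no fixed window. For this outcome the plan gives no exposure adjustment, no censoring rule and no denominator (all randomised, or converters only).

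**The concern.** A yes/no comparison of recurrence is fair only if both arms are watched for the same length of time. Here each fetus is at risk from its own conversion to its own delivery. Randomisation balances gestational age at entry (above 12 to below 36 weeks, section 7.2), but conversion and delivery both follow treatment. Section 1 expects faster cardioversion to go with more normal term deliveries, so the better drug may gain exposure at both ends.

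The open denominator adds a second problem. Only converters can recur. If all randomised participants are counted, a fetus that never converts scores as having no recurrence, which favours the drug that converts fewer.

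At stake is a secondary finding that a drug converts faster but holds the rhythm less well, when part or all of that contrast is exposure.

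**Working it through.** **Inputs from the documents.** First-month recurrence comes from section 2.5: "Recurrence of SVT and AF was documented in 8% and 15% of cases during the first month of maintenance treatment". The same section gives median conversion times by first-line drug. For SVT they are 3 days (digoxin), 4 days (flecainide) and 12 days (sotalol). For AF the median is 12 days with sotalol and was not reached before delivery with the other drugs. Section 3.2 gives 93 per arm (RCT A and C) and 89 per arm (RCT B).

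**The plan's own figure.** There is no sample size, event count or power for recurrence. The primary-outcome sizes reproduce with the pooled two-proportion formula, two-sided 0.05 and 80% power: 30% vs 50% gives 93, and 55% vs 75% gives 89. Only the 93 is used below, as a denominator.

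**Assumptions.** The documents do not give mean time at risk or the number of converters by arm. The values below are mine, and they are shown as a range.

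**Step 1: constant hazard, same in both arms.** Daily hazard h = −ln(1 − r)/30.
- SVT: −ln(0.92)/30 = 0.00278
- AF: −ln(0.85)/30 = 0.00542

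Cumulative recurrence over t days is 1 − exp(−h·t). The odds ratio compares the longer-exposed arm with the shorter. The true hazard ratio is 1 throughout.

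| Days at risk | SVT recurrence | SVT OR | AF recurrence | AF OR |
|---|---|---|---|---|
| 60 vs 51 | 15.4% vs 13.2% | 1.19 | 27.8% vs 24.1% | 1.21 |
| 56 vs 42 | 14.4% vs 11.0% | 1.36 | 26.2% vs 20.3% | 1.39 |
| 56 vs 28 | 14.4% vs 7.5% | 2.08 | 26.2% vs 14.1% | 2.16 |

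**Step 2: simulation with equal hazards.** This used 4,000 runs, 75 vs 60 converters and gamma-distributed follow-up with the means shown. The false-positive rate is that of the logistic Wald test at 5%.

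| Mean days at risk | SVT OR | SVT false positives | AF OR | AF false positives |
|---|---|---|---|---|
| 56 vs 56 | 1.00 | 3.5% | 1.00 | 4.5% |
| 60 vs 51 | 1.19 | 5.4% | 1.19 | 6.6% |
| 56 vs 42 | 1.38 | 5.9% | 1.41 | 9.6% |
| 56 vs 28 | 2.15 | 18% | 2.20 | 36% |

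In the same constant-hazard simulations, a time-to-event analysis gave hazard ratios of 0.99 to 1.05 and log-rank false-positive rates of 4.3% to 5.5%.

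**Step 3: all recurrence risk in the first 30 days.** With unequal follow-up, the logistic odds ratio falls to 1.03 to 1.30, and its false-positive rate does not exceed about 5.4%.

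**Step 4: all randomised as denominator.** Take 93 per arm, 75 vs 60 converters, and equal recurrence per converter.
- AF: 75 × 0.15/93 = 12.1% vs 60 × 0.15/93 = 9.7%, OR 1.28
- SVT: 75 × 0.08/93 = 6.5% vs 60 × 0.08/93 = 5.2%, OR 1.27

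This counts against the drug that converts more, even with no difference in time at risk.

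**Step 5: which sub-study.** RCT B compares digoxin with flecainide, whose medians differ by one day. At 60 vs 59 days the SVT figures are 15.4% vs 15.1%, OR 1.02, so conversion time adds almost nothing there. In RCT A the contrast is 12 days against a median not reached. In RCT C both arms contain digoxin, and the documents give no conversion times for the combinations. These medians describe treated cases, including those that never convert, so they do not themselves fix time at risk among converters.

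**The case against.** **The plan is not settled on a binary test.** Section 7.10 uses time-to-event language, and 7.11 says that secondary outcomes are also expressed as binary, which could mean in addition. This stands in part: the two sections are inconsistent. But 7.11 is where the tests are assigned, and it gives recurrence no other method.

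**The distortion may be small.** This stands. Section 2.5 reports the first month only, so a constant hazard beyond it is an assumption. With risk confined to that month, or a gap of about nine days, the false-positive rate stays near nominal.

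**Larger figures that a reader might infer.** Comparing 28 with 63 days at risk gives an odds ratio of about 2.4 to 2.5, but that contrasts two pregnancies. Nothing in the documents supports a 35-day difference between arm means. The 3-versus-12-day gap in section 2.5 is digoxin against sotalol in SVT, which no sub-study compares. Nor can a 20-point gain in term births be turned directly into extra recurrences. Sections 2.3 and 2.5 link preterm delivery mainly to incomplete arrhythmia control, and fetuses that never convert contribute no maintenance time.

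**The intention-to-treat rule and permanent cardioversion may already cover this.** Intention-to-treat counting does not repair the binary test (step 4). Time to permanent cardioversion, classified by final outcome, overlaps with an all-randomised measure. It is not the same as recurrence-free to birth, because a fetus that relapses and reconverts can still count as converted.

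**Conclusion.** The point holds as an inconsistency between 7.10 and 7.11, with a bias whose direction is predictable when recurrence hazard is equal and sustained. The binary test counts against the drug that converts sooner and prolongs pregnancy. With all randomised as denominator, it also counts against the drug that converts more.

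The documents do not fix the size. Under constant hazards the odds ratio is about 1.2 for a 9-day gap, 1.4 for 56 vs 42 days and 2.1 to 2.2 for 56 vs 28 days. It is about 1.0 to 1.3 if risk ends after the first month. RCT A deserves most attention, and conversion time adds little in RCT B. A reader might infer that the recurrence result is bound to mislead, or that the trial's main conclusion is at risk. The documents support neither: this is one secondary outcome, and the primary analysis and sample size are untouched.

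**What to change.** Align 7.11 with 7.10:

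- Move recurrence to the time-to-event list. Analyse time from sustained conversion (at least 24 hours, as in 7.7) to first confirmed recurrence by Kaplan-Meier and PROC PHREG, censored at birth. Treat demise as a competing event or address it in a sensitivity analysis.
- Date recurrence by the encounter at which it is documented. Section 7.8 lists the cardioversion date and the rhythm at each dated encounter, but no separate recurrence date.
- Label the result a non-randomised comparison among converters, and state that denominator.
- Report alongside it, for all randomised, the proportion converted and recurrence-free to birth.

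The cost is analysis-plan wording: conversion, encounter and birth or demise dates are already collected, and PROC PHREG is already planned. There are two small downsides. The hazard ratio among converters is conditional on a post-randomisation event, so it removes the exposure bias but not selection. Recurrence onset is interval-censored, because maintenance encounters are 1 to 3 weeks apart.

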**3.2 SAMPLE SIZE CALCULATIONS.** Based on our survey results and the retrospective study by [name] et al, we expect 70% of SVA cases to be SVT (50% no hydrops; 20% hydrops) and 30% AF (25% no hydrops; 5% hydrops). Survey II suggests that an average of 2.3 SVT/no hydrops, 1.21 AF/no hydrops and 1.03 treated SVT/hydrops cases/year/center will be eligible for RCT enrolment, with average consent rates of 81%. Sample size calculation for 2-arm treatment comparisons was performed using PASS (Power and Sample Size) v12 (NCSS, LLC, Kaysville, Utah, USA). To calculate sample size requirements for this study we expected the proportion of patients with normal primary outcome to be 55% with SVT without hydrops, 30% with AF without hydrops, and 30% of SVT with hydrops with the inferior treatment arm (i.e. the null hypothesis). We aim to detect an improvement of +20% in the proportion of patients with a normal primary outcome with the superior RCT arm (i.e. 75% for SVT without hydrops; 50% for AF without hydrops and SVT with hydrops; i.e. the alternative hypothesis). The test statistic used is the two-sided Likelihood Ratio test which is equivalent to the Wald chi-square for logistic regression models which will be used to analyze our primary outcome. The significance level of the test of significance was targeted at 0.05, with a power of 80%. Assuming those metrics, we will need 550 RCT participants, with a minimum number of patients in each of the three RCTs of:

**AF without hydrops (RCT A):** 186 (93/arm) treated cases ← 232 approached cases with 80% consent rate

**SVT without hydrops (RCT B):** 178 (89/arm) treated cases ← 222 approached cases with 80% consent rate

**SVT with hydrops (RCT C):** 186 (93/arm) treated cases ← 232 approached cases with 80% consent rate

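### Section 7.11 tests death with the logistic Wald chi-square, which cannot show a difference or give a usable odds ratio if one arm has no deaths

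*Combined protocol and SAP*

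**What the plan says.** Section 7.11 compares the primary outcome between arms by logistic regression. The likelihood-ratio test is given to model fit. The "Wald chi-square test from maximum likelihood estimates" decides whether the therapy arm is significant, and the estimate and its standard error become an odds ratio with 95% CI. Binary secondary outcomes follow the same method, and death is named: "death <1 month; etc.) will be assessed between the different therapy arms in the same way as the primary outcome". Section 7.10 lists a further binary death outcome, "Proportion of participants with arrhythmia related death", which falls under the same rule.

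Mortality is also analysed over time ("timing of mortality from initiation of therapy") with Kaplan-Meier curves and PROC PHREG. There, significance rests on "maximum likelihood estimates chi-square to determine statistical significance of the therapy arm".

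Three other statements bear on the point:

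- Section 7.11 specifies "All statistical analyses using SAS (SAS Institute, Cary NC) with standard settings". It names no exact or penalised method for any outcome, and each RCT is analysed separately.
- Fisher's "exact test for categorical variables" appears in 7.11 only for the baseline test of randomization.
- Section 3.2 describes the sample-size test as the "Likelihood Ratio test which is equivalent to the Wald chi-square for logistic regression models".

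**The concern.** When one arm has no events, the maximum likelihood odds ratio is not finite. The fitted log odds ratio keeps growing as the algorithm iterates, its standard error grows faster, and the ratio of the two goes to zero. The Wald test then returns a p-value near 1, even if the other arm has many deaths.

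The mortality figures in the plan make an empty arm possible. Without hydrops they are 0%-4% (section 2.1) or 0%-5% (section 2.6). For SVT with hydrops, section 2.5 cites a clinical report with no mortality on primary digoxin plus flecainide, which is one arm of RCT C. Sections 2.5 and 2.6 give 21% and about 20% for hydropic fetuses overall.

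If an arm has no deaths, the stated rule reports no difference and the promised odds ratio and CI do not exist. The analyst would notice, and would have to choose another method after seeing deaths by arm in an open-label trial.

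**Working it through.** **Inputs.** From section 3.2: 93 per arm (RCTs A and C), 89 per arm (RCT B), two-sided alpha 0.05, power 80%. Mortality rates are those cited above. The exact true rates used below are assumptions, shown as a range.

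**Step 1: reproduce the planned size.** n per arm = [1.96·√(2p̄(1−p̄)) + 0.8416·√(p1(1−p1)+p2(1−p2))]² / (p1−p2)².

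- 30% vs 50%: (1.358 + 0.571)² / 0.04 = 93.0, so 93.
- 55% vs 75%: (1.322 + 0.555)² / 0.04 = 88.1, so 89.

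Both match the plan. At these rates no cell is sparse, and treating the Wald and likelihood-ratio tests as interchangeable is reasonable.

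**Step 2: Wald test with an empty arm.** With a and b deaths in arms of n, log OR = ln[b(n−a) / (a(n−b))] and SE = √(1/a + 1/b + 1/(n−a) + 1/(n−b)). At a = 0 both are infinite, so the program reports the values at which it stops iterating. Fisher scoring from zero with a relative gradient stop of 1e-8, n = 93:

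| Deaths | log OR | SE | Wald p | Fisher p | Risk difference, Newcombe 95% CI (points) |
|---|---|---|---|---|---|
| 0 vs 6 | 18.5 | 4168 | 0.997 | 0.029 | 6.5 (1.2 to 13.4) |
| 0 vs 9 | 19.0 | 4168 | 0.996 | 0.003 | 9.7 (3.7 to 17.4) |
| 0 vs 19 | 18.8 | 2528 | 0.994 | 1.4e-6 | 20.4 (12.4 to 29.7) |

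Stopping one iteration earlier gives Wald p of 0.994, 0.994 and 0.991. At convergence it is at least 0.989 for every count from 1 to 93 in the other arm. In simulated survival data with 0 vs 9 deaths, the chi-square on the PHREG estimate gave p = 0.9999 and the log-rank test p = 0.002.

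**Step 3: chance of an empty arm.** P0 = (1−r)^n in one arm; for exactly one empty arm at equal rates, 2·P0·(1−P0).

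- RCT A (n = 93), r = 1/2/3/4%: exactly one arm empty 48/26/11/4%. RCT B (n = 89): 48/28/12/5%.
- RCT C, digoxin plus flecainide arm, r = 1/2/3/5%: chance of 0/93 is 39/15/6/0.8%.

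**Step 4: power in RCT C.** All pairs of binomial counts were enumerated at n = 93 per arm, two-sided 0.05, with a zero cell counted as not significant for Wald.

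| True death rates | Wald | Fisher |
|---|---|---|
| 0% vs 10% | 0% | 91% |
| 1% vs 10% | 39% | 72% |
| 1% vs 20% | 60% | 99.7% |
| 2% vs 20% | 84% | 98.5% |
| 3% vs 10% | 38% | 39% |
| 3% vs 20% | 91.2% | 95.8% |
| 5% vs 20% | 87.5% | 85.1% |
| 10% vs 21% | 52.8% | 47.7% |

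**Step 5: size under no difference.** Fisher: 0.4% at a 2% rate, 1.9% at 5%. Likelihood ratio: 9.4% and 6.7%.

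**The case against.** The strongest reply is that this will rarely matter. The zero for digoxin plus flecainide comes from one report, quoted without a denominator. Section 5.1 itself says that perinatal death is not unusual in hydropic fetuses whatever the treatment, and section 2.1 cites mortality of up to 35%. Once the true rate reaches 5%, an empty arm of 93 has a chance under 1%, and Fisher's test is then slightly less powerful than Wald. This stands, and it limits the power argument to true rates of about 0-2%.

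In RCTs A and B, Fisher's test needs 0 vs 6 deaths to reach 0.05 (0 vs 5 gives 0.059). At equal true rates of 1-4%, an empty arm together with a significant Fisher result has a chance of only 0.03-0.8%. This also stands: the loss there is the odds ratio and its CI, not a missed difference.

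A third reply is that the deaths would be visible anyway, in frequencies by arm, in Kaplan-Meier curves, in DSMB review, and in the likelihood-ratio test already printed (0 vs 6: p = 0.0035 in an arm-only model). They would be visible, but none of these replaces the stated decision rule or supplies a usable interval. The likelihood-ratio test is also anti-conservative at these rates (step 5).

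A reader might extend the point to delivery without SVA termination, because section 2.5 gives 5% (SVT) and 6% (AF) for arrhythmia persisting to birth. The documents do not support that. These figures are one part of an additive composite (32 + 8 + 5 = 45% for SVT) that counts preterm deliveries separately, including any with SVA still present. They do not show that the outcome is rare.

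**Conclusion.** The concern holds for death before one month and, by the same rule, for arrhythmia-related death. With an empty arm the stated test returns p of about 0.99 regardless of the data, and the planned odds ratio and CI are unusable. This is a stated rule that fails, not merely missing detail.

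Its practical size depends on the true rates, which are assumed here. In RCTs A and B the effect is mainly the lost interval estimate. In RCT C the power loss is large only when the lower arm is at about 0-2%, nearly disappears at 3% vs 10%, and reverses slightly at 5% or more.

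The PHREG part depends on reading its estimate-based chi-square as the Wald test, which is the natural reading but is not spelled out. A reader might infer that RCT C is likely to have an empty arm, or that its mortality comparison has no power. The documents support neither, since they give one zero without a denominator and about 20% overall. The primary outcome, at assumed rates of 30-75%, is not affected.

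**What to change.** Add to section 7.11:

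- For death before one month and arrhythmia-related death, compare all randomised participants by arm with Fisher's exact test, and report the risk difference with a Newcombe 95% CI. Do this in each RCT whatever counts are seen, so that the choice of method does not depend on the data.
- For time to death, use the log-rank test for significance, and report the hazard ratio only if both arms have deaths.

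In section 3.2, limit the statement that the two tests are equivalent to the primary outcome. Leave the primary analysis and the other secondary outcomes as they are.

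This costs two or three sentences, with no new data, endpoint or sample size, and intention-to-treat is kept. The statistical price is that Fisher's test is conservative when deaths are few (step 5) and gives up about 2-5 points of power at ordinary hydrops mortality: 87.5 − 85.1 = 2.4 points at 5% vs 20%, and 52.8 − 47.7 = 5.1 points at 10% vs 21%.
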